2 SYNOPSIS OF PROPOSED DIAGNODE-2 STUDY

Name of Sponsor/Company Diamyd Medical AB	Individual Study Table Referring to Part of Dossier in which the Individual Study or Study Table is Presented: Volume: Reference:	(For National Authority Use Only)
Name of Finished Product: DIAMYD® D-vitamin ██████████ ██████████		
Name of Active Ingredient: ██████████ ██████████ ██████████		
Title of Study: A Phase IIb, 2-Arm, Randomized, Double-blind, Placebo-Controlled, Multicentre Study to Optimize Diamyd® Therapy Administered into Lymph Nodes Combined with Oral Vitamin D to Investigate the Impact on the Progression of Type 1 diabetes		
Protocol Number: DIAGNODE-2 ██████████		
Investigators and Study Centre: Approximately 22 sites in Sweden, Spain, Czech Republic and the Netherlands including approximately 106 patients		
Phase of Development: Phase IIb		
Objectives: Primary objective The primary objective is to evaluate the efficacy of Diamyd, administered into lymph nodes in combination with an oral vitamin D regimen, compared to placebo in terms of preserving endogenous insulin secretion as measured by C-peptide. Secondary objectives The secondary objectives are to compare Diamyd, administered into lymph nodes in combination with an oral vitamin D regimen and placebo treatment with respect to the effects on the diabetes status, treatment safety, immune system and quality of life (QoL) of the patients.		
Study Design: The study is a 2-arm, randomized, double-blind, placebo-controlled, multicenter, clinical trial. Eligible patients will receive injections of Diamyd/placebo into an inguinal lymph gland at three occasions, with one month intervals in combination with an oral vitamin D/placebo regimen (starting 1 month ahead of injections) during 4 months. All patients will continue to receive intensive insulin treatment from their personal physicians during the whole study period. The patients will be followed in a blinded manner for a total of 15 months. All patients that are ongoing, i.e. have not performed Visit 7 (15 months visit) when protocol version 7 is approved and implemented, will be asked to participate in the Extension Study Period which include Visit 8 at month 24.		
Selection of Patients: Patients must be ≥ 12 and < 25 years old, and diagnosed with Type 1 diabetes (T1D) within the previous 6 months at the time of screening. Patients will be eligible for enrolment if fasting C-peptide is ≥ 0.12 nmol/L (0.36 ng/mL) and elevated levels of GAD65A, i.e. antibodies to glutamic acid decarboxylase (GAD) with molecular weight of 65 kDa (GAD65) are present.		
Number of Patients Planned: Approximately 106 patients will be enrolled. To ensure that 106 patients are screened and enrolled approximately 127 patients will be screened.		

Name of Sponsor/Company Diamyd Medical AB	Individual Study Table Referring to Part of Dossier in which the Individual Study or Study Table is Presented: Volume: Reference:	(For National Authority Use Only)
Name of Finished Product: DIAMYD® D-vitamin [REDACTED] [REDACTED]		
Name of Active Ingredient: [REDACTED] [REDACTED] [REDACTED]		
Description of Treatment Groups: The patients will be assessed for eligibility at the screening visit (Visit 1) 2 to 4 weeks prior to start of oral treatment with vitamin D. On Visit 2 (Day 1), patients eligible for the study will be randomized to 1 of 2 treatment groups: 
• Approximately 53 patients will be assigned to receive i) three (3) intralymphatic injections with 4 µg Diamyd on Days 30, 60, and 90 and; ii) oral vitamin D 2000 IE daily for 4 months (from Day 1 through Day 120)• Approximately 53 patients will be assigned to receive i) three (3) intralymphatic injections of Placebo for Diamyd on Days 30, 60, and 90 and; ii) oral Placebo for vitamin D once a day for 4 months (from Day 1 through Day 120)		

Name of Sponsor/Company Diamyd Medical AB	Individual Study Table Referring to Part of Dossier in which the Individual Study or Study Table is Presented: Volume: Reference:	(For National Authority Use Only)
Name of Finished Product: DIAMYD® D-vitamin ██████████ ██████████		
Name of Active Ingredient: ██████████ ██████████ ██████████		

Endpoints:
 
Primary Endpoint:
 
 Change in C-peptide (Area Under the Curve [AUC]_{mean 0-120 min}) during a Mixed Meal Tolerance Test (MMTT) between baseline to 15 months. 
Key Secondary Endpoints:
 
 Change in insulin-dose-adjusted HbA1c (IDAA1c) between baseline and 15 months Change in Hemoglobin A1c (HbA1c) between baseline and 15 months Change in daily exogenous insulin consumption between baseline and 15 months. 
Secondary endpoints:
 
 Other variables that indicate Diabetes Status such as plasma C-peptide, variability of blood sugar, and number of self-reported hypoglycemia. Variables that indicate treatment safety such as occurrence of adverse events (AEs), physical examinations, hematology, urine analysis, injection site reactions, GAD65A titer, vital signs and clinical chemistry. Variables that indicate effects on the immune system such as serum autoantibodies (and isotypes) to GAD65, serum cytokine levels, secretion of cytokines by immune cells in response to GAD65-stimulation, and proportions of immune cells in blood. Measurements of patient QoL by questionnaire. 
Exploratory Endpoints:
 
 All data collected at the 24-month follow-up visit will be regarded as exploratory endpoints. 
Sample size:
 
A total sample size of 106 patients is planned for a 1:1 randomization in order to provide 90% power to detect a 50% difference in geometric mean C-peptide (AUC_{mean 0-120 min}) at 15 months between the active arm and placebo arm using a two-sided test at the 0.05 level, with 10% loss to follow-up. This is based upon a t-test employing ln(X+1) normalizing transformation of C-peptide (AUC_{mean 0-120 min}) during an MMTT at 15 months and assumed mean and standard deviation estimates, on the transformed scale, of 0.134 and 0.20 respectively.
 
Analysis of Primary endpoint variable:
 
The mean change in log-transformed values will be analyzed using Mixed Model Repeated Measures (MMRM). The model for analysis will include fixed, categorical effects of treatment, randomization strata (GAD65A level), visit and treatment by visit interaction, as well as the continuous, fixed covariates of baseline value.
 
Analysis of Key Secondary endpoint variables:
 
Key secondary efficacy endpoint variables will be analysed with the same MMRM model as the primary efficacy endpoint.
 
Analysis of Secondary endpoint variables:
 
Continuous secondary diabetes status variables will be compared using the same MMRM model as for the primary efficacy endpoint.
		

Name of Sponsor/Company Diamyd Medical AB	Individual Study Table Referring to Part of Dossier in which the Individual Study or Study Table is Presented: Volume: Reference:	(For National Authority Use Only)
Name of Finished Product: DIAMYD® D-vitamin ██████████ ██████████		
Name of Active Ingredient: Recombinant Human Glutamic Acid Decarboxylase (rhGAD65) Calciferol		

Categorical secondary endpoints will be presented using summary statistics and p-value from stratified Cochran/Mantel-Haenszel Test.
 
For immunological secondary endpoints summary statistics will be accompanied with p-values from non-parametric statistical tests
 
Analysis of the QoL data obtained within the study will follow the EQ-5D-5L User guide.
		

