4.1.1 GAD and Diamyd, Completed Studies

Although the involvement of GAD in neural transmission is understood by its function as an enzyme converting glutamate to gamma-amino butyric acid (GABA), its specific and unequivocal function in pancreatic beta cells, as well as its role in the pathogenesis of either form of diabetes remains unclear. Indeed, the reason why GAD is a major autoantigen in autoimmune diabetes is not known. However, a broad body of the scientific community has produced convincing data from the non-obese diabetic (NOD) mouse model of T1D that administration of an isoform of GAD with a molecular mass of approximately 65kDa (GAD65) can prevent autoimmune destruction of pancreatic beta cells and subsequent need for exogenous insulin replacement^{9,10,11,12,13,14,15,16,17,18,19}. These findings indicate the potential of Diamyd administration as a treatment for T1D.

GAD65 is a major autoantigen in autoimmune diabetes and clinical administration of Diamyd aims to intervene in the autoimmune process in T1D by modulating the immune system via discrete, antigen-specific tolerization in order to arrest or delay the autoimmune destruction of pancreatic beta cells. In recent-onset T1D patients, such induced immune tolerization is proposed to prevent the destruction of remaining beta cells thereby maintaining residual insulin secretion, improving metabolic control and reducing the risk of acute and long-term diabetes complications. Available data demonstrate that even relatively modest retained insulin secretion capability is associated with clinically meaningful benefits including improved glycemic control, reduced hypoglycemia, retinopathy and nephropathy^{1,2,3,4}. Additionally, intervening in the destruction of beta cells could allow for beta cell replenishment, either by stimulating regeneration or transplantation²⁰.

Thus, the goal of Diamyd therapy would be to dramatically slow or halt the ongoing autoimmune destruction of pancreatic islet beta cells in order to preserve the largest possible amount of endogenous insulin production.

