13 STATISTICAL METHODS

13.1 Estimation of Sample Size

A total sample size of 106 patients is planned for a 1:1 randomization in order to provide 90% power to detect a 50% difference in geometric mean C-peptide ($AUC_{\text{mean } 0-120 \text{ min}}$) during an MMTT at 15 months between the active arm and placebo arm using a two-sided test at the 0.05 significance level. The sample size has been adjusted to allow for 10% loss to follow-up. This is based upon a t-test employing $\ln(X+1)$ normalizing transformation of C-peptide ($AUC_{\text{mean } 0-120 \text{ min}}$) during an MMTT at 15 months and assumed mean and standard deviation estimates, on the transformed scale, of 0.134 and 0.20, respectively¹

It is estimated that there will be a screening failure rate of 16%. To ensure that 106 patients are screened and enrolled approximately 127 patients will be screened.

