13.2.3 Hypotheses and Statistical Methods

13.2.3.1 Analysis of Primary Endpoint Variable

The primary efficacy variable will be change in log-transformed C-peptide AUC_{mean 0-120 min} during an MMTT from baseline to Month 15. Mean changes from baseline will be analyzed using Mixed Model Repeated Measures (MMRM). The model for analysis will include fixed, categorical effects of treatment, randomization

strata (GAD65A level), visit and treatment by visit interaction, as well as the continuous, fixed covariates of log-transformed baseline C-peptide $AUC_{\text{mean } 0-120}$ during an MMTT. An unstructured (co)variance structure will be used to model the within-patient errors. If this analysis fails to converge, compound symmetry will be tested. The (co)variance structure converging to the best fit, as determined by Akaike's information criterion will be used as the primary analysis. The Kenward-Roger approximation will be used to estimate denominator degrees of freedom. The primary treatment comparison will be the contrast between treatments at Month 15 for active treatments versus placebo.

Least Square (LS) Mean estimates and 95% confidence intervals (CIs) will be back-transformed from the log scale to the original scale and given together with nominal p-values. Back-transformed estimates of the treatment difference will provide an estimate of the (Diamyd/placebo)-ratio in the relative change from baseline in AUC. Here a ratio of e.g. 0.8 will mean that the change from baseline to month 15 in C-peptide level was 20% smaller for Diamyd than for placebo at Month 15.

A sensitivity analysis where the hypotheses will also be assessed using Analysis of Covariance (ANCOVA) adjusted for baseline value of C-peptide ($AUC_{\text{mean } 0-120 \text{ min}}$) during an MMTT between baseline to 15 months and randomization strata (GAD65A level) using the completers set.

Further sensitivity analyses will be given in the SAP.

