13.2.3.2 Analysis of Secondary Endpoint Variables

13.2.3.2.1 Key Secondary Variables of Diabetes Status

The following key secondary efficacy endpoint variables will be analysed with the same model (MMRM) as the primary efficacy endpoint:

- Change in IDAA1c between baseline and 15 months.
- Change in HbA1c between baseline and 15 months.
- Change in daily exogenous insulin consumption between baseline and 15 months.

The analysis of key secondary endpoints will be subject to the same sensitivity analyses as the primary efficacy analysis. However, exploration of key secondary endpoints by covariate and subgroups analyses will be based on the observed results for respective endpoint.

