13.2.5 Adjustment for Covariates

Change from baseline analyses will be adjusted for baseline and all other analyses will be adjusted for randomization strata (GAD65A level).

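### Baseline MMTT C-peptide is unused in the models for IDAA1c, HbA1c and insulin dose; adding it beside each endpoint's own baseline is a modest, nearly free gain in precision

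*Protocol*

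**What the plan says.** The synopsis (section 2) describes the primary MMRM with treatment, GAD65A stratum, visit, treatment by visit, and a continuous covariate that it calls only the baseline value. It then says "Key secondary efficacy endpoint variables will be analysed with the same MMRM model as the primary efficacy endpoint".

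Section 13.2.3.1 fills in that covariate for the primary variable: "continuous, fixed covariates of log-transformed baseline C-peptide" AUC. Section 13.2.3.2.1 applies the model to change in IDAA1c, HbA1c and daily insulin: "The following key secondary efficacy endpoint variables will be analysed with the same model (MMRM) as the primary efficacy endpoint". It does not repeat which baseline enters.

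Section 13.2.5 gives the general rule: "Change from baseline analyses will be adjusted for baseline and all other analyses will be adjusted for randomization strata (GAD65A level").

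Section 13.2.4 places the three endpoints at steps 2 to 4 of a fixed testing sequence. Table 2 and section 7.1.1.4 schedule an MMTT with C-peptide for every patient at Visit 2. Section 10.1.1 stratifies randomization by country and GAD65A level only.

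**The concern.** The protocol's own rationale ties residual beta-cell function to these endpoints. Section 4.1 describes growing reliance on exogenous insulin as endogenous production falls, which bears on insulin dose and so on IDAA1c. Section 4.1.1 says that "even relatively modest retained insulin secretion capability is associated with clinically meaningful benefits including improved glycemic control", which bears on HbA1c. It is therefore plausible that baseline MMTT C-peptide carries information about Month 15 values beyond what each endpoint's own baseline carries. The measurement will already be in the database, but no key secondary model uses it.

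Baseline secretion may also vary widely. Section 8.1 sets a floor for fasting C-peptide but no ceiling, admits ages 12 to under 25, and allows up to 6 months since diagnosis. With about 53 patients per arm and no stratification on C-peptide, a chance imbalance in residual function is possible, and only the model could take account of it.

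The stake is precision. The sample size in section 13.1 is set for the primary endpoint alone and no power is stated for the other three. In a fixed sequence, one miss ends confirmatory testing of what follows.

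**Working it through.** **Which baseline is in the model.**
- Synopsis: a generic baseline value.
- 13.2.3.1: log baseline C-peptide AUC, which is the primary variable's own baseline.
- 13.2.3.2.1: the same model, applied to three change-from-baseline endpoints.
- 13.2.5: change-from-baseline analyses are adjusted for baseline.

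The consistent reading is that each endpoint is adjusted for its own baseline. Baseline C-peptide is then not a covariate for IDAA1c, HbA1c or insulin dose.

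**The plan's own figure.** Section 13.1 states "A total sample size of 106 patients is planned for a 1:1 randomization", with "90% power to detect a 50% difference in geometric mean C-peptide", "using a two-sided test at the 0.05 significance level", values of 0.134 and 0.20 on the transformed scale, and 10% loss. Using 0.134 as the difference:

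n per arm = 2 × (1.960 + 1.282)² × 0.20² / 0.134² = 46.8, so 47. Then 47 / 0.90 = 52.2, so 53 per arm and 106 in total.

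The figure reproduces on that use of 0.134. It concerns the primary endpoint and sets no power for the key secondaries.

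**Gain from adding baseline C-peptide.** The protocol gives no SD, power or correlation for the key secondaries, so the following are assumptions:
- r is the partial correlation of log baseline C-peptide AUC with the Month 15 endpoint, given the endpoint's own baseline, taken from 0 to 0.4.
- The starting power of 80% is illustrative. About 53 × 0.90 = 47.7, or 48, patients per arm are evaluable.

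Formulas: residual variance ratio = 1 − r²; SE reduction = 1 − √(1 − r²); power = Φ(2.802 / √(1 − r²) − 1.960), where 2.802 = 1.960 + 0.842; equivalent extra patients = 106 / (1 − r²) − 106.

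| r | Variance ratio | SE reduction | Power, from 80% | Equivalent extra patients |
|---|---|---|---|---|
| 0 | 1.00 | 0% | 80.0% | 0 |
| 0.1 | 0.99 | 0.5% | 80.4% | 1.1 |
| 0.2 | 0.96 | 2.0% | 81.6% | 4.4 |
| 0.3 | 0.91 | 4.6% | 83.6% | 10.5 |
| 0.4 | 0.84 | 8.3% | 86.4% | 20.2 |

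**Why these are upper limits for each r.** The formula 1 − r² is that of a single-visit analysis of covariance. The planned MMRM has a baseline main effect and no baseline-by-visit term, so one slope would serve all visits. Table 2 measures HbA1c at Months 1, 2, 3, 6 and 15. If baseline C-peptide matters more at Month 15 than at Month 1, a common slope fits Month 15 imperfectly and recovers less than 1 − r² implies. A by-visit interaction removes that constraint.

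**The case against.** The strongest reply is that nothing here is wrong. Omitting a second prognostic covariate from a prespecified randomized comparison causes no bias and does not inflate the type I error. The unadjusted standard error already allows for chance imbalance on average. The same suggestion could be made about age or time since diagnosis. Section 4.1.1 reports an association; it does not say that baseline C-peptide predicts Month 15 HbA1c or insulin dose once their own baselines are known. The correlation range is assumed, and up to r = 0.3 the standard error falls by less than 5%. All of this stands, and it limits the point to a modest improvement.

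It can also be said that section 13.2 leaves detail to the SAP, which is not shown, and that 13.2.3.2.1 already foresees exploratory covariate analyses. The SAP may indeed name the covariates. But section 13.2 also binds the SAP to follow the protocol's outline, and that outline already gives these endpoints a model. An exploratory covariate analysis would not change the test used in the sequence.

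A reader might go further and infer from 13.2.3.1 and 13.2.3.2.1 that HbA1c, IDAA1c and insulin dose are adjusted for baseline C-peptide and not for their own baselines. That would cost more. If baseline C-peptide were uninformative (the worst case), the variance would rise by a factor 2/(1 + ρ) for a baseline-to-Month-15 correlation ρ: 1.54, 1.33 and 1.11 at ρ = 0.3, 0.5 and 0.8, taking 80% power to 62%, 68% and 76%. The documents do not support this reading. The synopsis uses the generic term, 13.2.3.1 merely supplies the primary variable's own baseline, and 13.2.5 adjusts change scores for baseline. Section 13.2.5 is not a perfect tie-breaker, because it assigns the GAD65A stratum to all other analyses while the primary change-from-baseline model contains both terms. It still points clearly to the endpoint's own baseline.

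**Conclusion.** The point holds as an inexpensive improvement, not as an error. The key secondary models are most naturally read as adjusting for each endpoint's own baseline, with wording that should be made explicit. They leave out baseline MMTT C-peptide, which the schedule collects before treatment and which the protocol's rationale relates to all three endpoints.

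The size rests on an assumed partial correlation: no gain at zero, and at most about 2%, 5% and 8% off the standard error at 0.2, 0.3 and 0.4. The power values start from an illustrative 80%, not from any figure in the protocol. The document shows neither a definite loss of power nor a biased treatment estimate, and neither should be claimed. The case for acting is that the cost is close to nothing and that these endpoints are steps 2 to 4 of the testing sequence.

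**What to change.** In section 13.2.3.2.1 and in the synopsis, state that each key secondary MMRM includes, besides the existing terms, two continuous covariates: the endpoint's own baseline value and log-transformed baseline MMTT C-peptide AUC. Preferably give each a by-visit interaction, so that the Month 15 slope is not forced to equal that at earlier visits. Settle this in the protocol or SAP before unblinding. If the sponsor prefers not to add C-peptide, the same sentence should still name the endpoint's own baseline, which removes the literal misreading.

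The cost is one sentence and no new data. Statistically it is one degree of freedom per model without interactions. With them, each covariate takes up to four more if all five post-baseline visits of Table 2 enter the model.

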3 LIST OF ABBREVIATIONS AND DEFINITION OF STUDY SPECIFIC TERMINOLOGY

1,25(OH)2D3	1 α ,25-dihydroxyvitamin D3 also called calcitriol
AE	Adverse Event
Alum	Aluminum hydroxide
ANCOVA	Analysis of Covariance
AUC	Area Under the Curve
AUC _{mean 0-120 min}	AUC mean 0-120 minutes
BMI	Body Mass Index
BP	Blood Pressure
DKA	Diabetic Ketoacidosis
CI	Confidence Interval
CRO	Contract Research Organization
DCCT	Diabetes Control and Complications Trial
DSMB	Data Safety Monitoring Board
eCRF	Electronic Case Report Form
eDiary	Electronic Diary
ELISPOT	Enzyme Linked Immunosorbent Spot Forming Cell Assay
FAS	Full analysis set
FGM	Flash Glucose Monitoring
GABA	Gamma-amino Butyric Acid
GAD	Glutamic acid decarboxylase
GAD65	GAD with molecular mass 65 kDa
GAD65A	Antibodies to GAD65
GCP	Good Clinical Practice
HbA1c	Hemoglobin A1c
HCG	Human Chorionic Gonadotropin
HIV	Human Immunodeficiency Virus
HLA	Human Leukocyte Antigen
IAA	Insulin Autoantibody
IA-2	Insulinoma-associated Protein 2

IA-2A	Insulinoma-associated Protein 2 antibodies
ICF	Informed Consent Form
ICH	International Council for Harmonisation of Technical Requirements for Pharmaceuticals for Human Use
IDAA1c	Insulin-Dose-Adjusted HbA1c
IEC	Independent Ethics Committee
IFN	Interferon
IgG	Immunoglobulin G
IgM	Immunoglobulin M
IL	Interleukin
IMP	Investigational Medicinal Product
IWRS	Interactive Web Response System
LADA	Latent Autoimmune Diabetes in Adults
LS	Least Square
MedDRA	Medical Dictionary for Regulatory Activities
MMRM	Mixed Model Repeated Measures
MMTT	Mixed Meal Tolerance Test
NCS/CS	Not Clinically Significant/Clinically Significant
NOD	Non-obese Diabetic
PBMC	Peripheral Blood Mononuclear Cells
PPS	Per-Protocol Set
QALY	Quality Adjusted Life Years
QoL	Quality of Life
rhGAD65	Recombinant Human GAD65
SAP	Statistical Analysis Plan
SAE	Serious Adverse Event
SOC	System Organ Class
SOP	Standard Operating Procedure
█	█
SUSAR	Suspected Unexpected Serious Adverse Reaction
T1D	Type 1 Diabetes
T2D	Type 2 Diabetes
TEAE	Treatment-Emergent Adverse Event
TESAE	Treatment-Emergent Serious Adverse Event
█	█
Th1	T Helper Cell Type 1
Th2	T Helper Cell Type 2
TNF	Tumour Necrosis Factor

